6.1.2 Serious Adverse Event (SAE)

Serious Adverse Event (SAE) means any untoward medical occurrence that results in any of the following outcomes:

- **Death.** Results in death.
- **Life-threatening.** Is life-threatening (refers to an AE in which the patient was at risk of death at the time of the event. It does not refer to an event which hypothetically might have caused death if it were more severe).

- **Hospitalization.** Requires inpatient hospitalization or prolongation of an existing hospitalization (see clarification in the paragraph below on planned hospitalizations).
- **Disability/incapacity.** Results in persistent or significant disability or incapacity. (Disability is defined as a substantial disruption of a person's ability to conduct normal life functions).
- **Pregnancy**
- **Congenital anomaly/birth defect:** Results in a congenital anomaly/birth defect in a neonate/infant born to a mother exposed to the IMP.
- **Medically important event.** This refers to an AE that may not result in death, be immediately life threatening, or require hospitalization, but may be considered serious when, based on appropriate medical judgment, may jeopardize the patient, require medical or surgical intervention to prevent one of the outcomes listed above, or involves suspected transmission via a medicinal product of an infectious agent. Examples of such medical events include allergic bronchospasm requiring intensive treatment in an emergency room or at home, blood dyscrasias or convulsions that do not result in inpatient hospitalization, or the development of drug dependency or drug abuse; any organism, virus, or infectious particle (e.g., prion protein transmitting transmissible spongiform encephalopathy), pathogenic or nonpathogenic, is considered an infectious agent.

6.1.3 Assessment of Severity of Adverse Events

The adverse event severity grading scale for the NCI CTCAE v5.0 will be used for assessing adverse event severity. The below table should be used for assessing severity for adverse events that are not specifically listed in the NCI CTCAE.

Adverse Event Severity Grading Scale for Events Not Specifically Listed in NCI CTCAE

Grade	Severity
1	Mild; asymptomatic or mild symptoms; clinical or diagnostic observations only; or intervention not indicated
2	Moderate; minimal, local, or non-invasive intervention indicated; or limiting age-appropriate instrumental activities of daily living ^a
3	Severe or medically significant, but not immediately life-threatening; hospitalization or prolongation of hospitalization indicated; disabling; or limiting self-care activities of daily living ^{b,c}

4	Life-threatening consequences or urgent intervention indicated ^d
5	Death related to adverse event ^d

NCI CTCAE = National Cancer Institute Common Terminology Criteria for Adverse Events.

Note: Based on the most recent version of NCI CTCAE v5.0 which can be found at: http://ctep.cancer.gov/protocolDevelopment/electronic_applications/ctc.htm

- a. Instrumental activities of daily living refer to preparing meals, shopping for groceries or clothes, using the telephone, managing money, etc.
- b. Examples of self-care activities of daily living include bathing, dressing and undressing, feeding oneself, using the toilet, and taking medications, as performed by patients who are not bedridden.
- c. If an event is assessed as a "significant medical event;" it must be reported as a serious adverse event.
- d. Grade 4 and 5 events must be reported as serious adverse events.

6.1.4 Attribution of an Adverse Event

All AEs and SAEs whether volunteered by the subject, discovered by study personnel during questioning, or detected through physical examination, laboratory test, or other means will be reported appropriately. Each reported AE or SAE will be described by its duration (i.e., start and end dates), regulatory seriousness criteria if applicable, suspected relationship to atezolizumab (see following guidance), and actions taken.

An assessment of the relationship between the adverse event and the medical intervention, using the following categories:

Definitely Related: *The AE is clearly related to the intervention.* There is clear evidence to suggest a causal relationship, and other possible contributing factors can be ruled out.

Probably Related: *The AE is likely related to the intervention.* There is evidence to suggest a causal relationship, and the influence of other factors is unlikely.

Possibly Related: *The AE may be related to the intervention.* There is some evidence to suggest a causal relationship (e.g., the event occurred within a reasonable time after administration of the trial intervention). However, the influence of other factors may have contributed to the event (e.g., the subject's clinical condition, other concomitant events).

Unlikely: *The AE is doubtfully related to the intervention.* A clinical event, including an abnormal laboratory test result, whose temporal relationship to drug administration makes a causal relationship improbable (e.g., the event did not occur within a reasonable time after administration

of the trial intervention) and in which other drugs or chemicals or underlying disease provides plausible explanations (e.g., the subject's clinical condition, other concomitant treatments).

Unrelated: *The AE is clearly NOT related to the intervention.* The AE is completely independent of study intervention, and/or evidence exists that the event is definitely related to another etiology.

To ensure consistency of AE and SAE causality assessments, investigators should apply the following general guideline:

Yes: Related (definitely, probably, possibly, unlikely)

There is a plausible temporal relationship between the onset of the AE and administration of the atezolizumab and/or radiotherapy and the AE cannot be readily explained by the subject's clinical state, intercurrent illness, or concomitant therapies; and/or the AE follows a known pattern of response to the study drug or with similar treatments; and/or the AE abates or resolves upon discontinuation of the atezolizumab and/or radiation therapy or dose reduction and, if applicable, reappears upon rechallenge.

No: Not Related (unrelated)

Evidence exists that the AE has an etiology other than the atezolizumab and/or radiation therapy (e.g., preexisting medical condition, underlying disease, intercurrent illness, or concomitant medication); and/or the AE has no plausible temporal relationship to atezolizumab administration (e.g., cancer diagnosed two days after first dose of study drug).

For patients receiving combination therapy, causality will be assessed individually for each protocol-mandated therapy.

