6.2.3 Reporting of Adverse Events and Serious Adverse Events

Sponsor-investigator will be responsible for collecting all protocol-defined adverse events (AEs)/serious adverse events (SAEs), pregnancy reports, other special situation reports, AESIs and product complaints with an AE where the patient has been exposed to the investigational product

Please refer to table 15 below to identify adverse events that meet reporting requirements.

All serious adverse events (SAEs) must also be documented in OnCore®.

Table 15

Attribution	SAE				AE			
	Grade 1, 2 & 3		Grade 4 and 5		Grade 3	Grade 4		
	Expected	Unexpected	Expected	Unexpected	Unexpected	Expected	Unexpected	
Unrelated Unlikely	IRB ¹ and DSMC ² - Routine Review ³	IRB ¹ and DSMC ² - Routine Review ³	IRB ¹ - Routine Review ³ DSMC ² - Within 5 calendar days	IRB ¹ - Routine Review ³ DSMC ² - Within 5 calendar days	DSMC ² - Routine Review ³	DSMC ² - Within 5 calendar days	DSMC ² - Within 5 calendar days	
Possible Probable Definite		IRB ¹ and DSMC ² - Within 5 calendar days FDA ⁴		IRB ¹ and DSMC ² - Within 5 calendar days FDA ⁴				

1. Guidance on adverse event reporting to the IRB is available online at MCW IRB Policies and Procedures.
2. For expedited DSMC reporting, study coordinator/research nurse must notify the DSMC via email including the subject ID, date of event, grade, relatedness, expectedness, and a short narrative. DSMC will review data entered into OnCore®.
3. For routine reporting, the events will be reported to IRB as part of the annual continuing progress report and the DSMC will review data entered into OnCore® at the time of scheduled monitoring.
4. Fatal or life-threatening SAEs meeting the criteria indicated in the above table will be reported to FDA no later than seven calendar days after study staff's initial awareness of the event. If the SAE is not fatal or life-threatening and meets the above criteria, the timeline for submitting an IND safety report to FDA is no later than 15 calendar days after study staff's initial awareness of the event. See section 6.2.3 for detailed reporting instructions.

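### Section 6.1.4 counts adverse events rated 'unlikely' as related, against its own definition of 'unlikely', Table 15 and section 6.2.4

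*Combined protocol and SAP*

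**What the plan says.** Section 6.1.4 defines five attribution categories: definitely, probably, possibly, unlikely and unrelated. An 'unlikely' event is one "whose temporal relationship to drug administration makes a causal relationship improbable", with other drugs, chemicals or underlying disease as a plausible explanation.

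The section then gives a yes/no rule, introduced by "To ensure consistency of AE and SAE causality assessments, investigators should apply the following general guideline". The two groups are "Yes: Related (definitely, probably, possibly, unlikely" and "No: Not Related (unrelated", with closing parentheses after each. The text under the yes group begins "There is a plausible temporal relationship between the onset of the AE and administration of the atezolizumab and/or radiotherapy" and adds further alternatives joined by and/or.

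Table 15 in section 6.2.3 sorts events into two attribution rows, "Unrelated Unlikely" and "Possible Probable Definite". Section 6.2.4 limits expedited IND safety reports to events that are serious, unexpected and at least possibly related to the study drug.

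Other sections use a bare 'related', 'unrelated' or 'attributed' without naming grades: the manufacturer report types in 6.2.3.1, the follow-up rule in 6.2.1, and the post-study SAE provisions in 6.2.1 and 6.2.2.9. No section says which grouping governs.

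**The concern.** The yes/no rule is there to make causality assessments consistent, but it places a category defined by improbable causation among the related events. The reporting table and the IND threshold place the same category on the other side. Two coordinators who both follow the protocol could therefore label one event differently.

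At stake is the meaning of 'related' wherever the protocol uses that word alone. The trial enrolls at most 18 patients after the restart of the TITE-CRM, so a few reclassified events would visibly change any count of related events.

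**Working it through.** There is no figure to recompute. The check sets the sections side by side and follows one event rated 'unlikely' through each.

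**1. Count of related categories.** Section 6.1.4: definitely, probably, possibly and unlikely, or 4 of 5. Table 15: possible, probable and definite, or 3 of 5. The difference is 4 − 3 = 1 category, exactly 'unlikely'. Section 6.2.4 sides with Table 15.

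**2. Consistency inside 6.1.4.** The text for the not-related group describes another etiology and/or the lack of a plausible temporal relationship to atezolizumab. The definition of 'unlikely' has both features in weaker form. The text for the related group offers three and/or routes: plausible timing with no ready alternative explanation, a known pattern of response, or improvement when treatment is stopped or reduced. The definition of 'unlikely' fits the not-related description better than the first of these routes.

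**3. Expedited reporting.** Table 15, for an unexpected SAE rated 'unlikely':

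| Grade | Table 15 applied to the five-level rating | 6.1.4 'related' label carried into Table 15 |
|---|---|---|
| 1–3 | IRB and DSMC routine review; no FDA report | IRB and DSMC within 5 calendar days; FDA report |
| 4–5 | IRB routine review; DSMC within 5 calendar days; no FDA report | IRB and DSMC within 5 calendar days; FDA report |

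For Grade 4–5 the DSMC timing is the same in both columns; only the IRB and FDA steps move. For expected SAEs and non-serious AEs, the table as extracted shows no separate entry in the related row, so no difference can be shown.

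**4. Sections that use only the binary word.** Here 6.1.4 supplies the only yes/no definition.

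- Section 6.2.3.1: a serious event goes to the manufacturer as a serious adverse drug reaction if related and as an other SAE if unrelated. The label changes; the deadline is 30 calendar days for both.
- Section 6.2.1: one sentence ties follow-up to resolution to relatedness, although another there describes follow-up to resolution without that condition. After the 12-month period, only SAEs attributed to study treatment are to be reported.
- Section 6.2.2.9: post-study SAEs are reported if believed related to earlier study drug exposure; deaths are reported whatever the cause.
- Any summary of related events would gain or lose every 'unlikely' event. Section 8 prespecifies no such summary.

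**5. Primary endpoint.** Under section 8.2.1 the toxicity and death criteria for a DLT require a probable or definite relationship, so an 'unlikely' event cannot meet them. The remaining criterion, failure to finish radiotherapy in time, sets no causality grade. It does except an unrelated death. Because the death criterion itself asks for probable or definite, I do not read a death rated 'unlikely' as becoming a DLT by this route.

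**The case against.** The strongest reply is that section 6.1.4 sets no reporting route. Section 6.2.3 sends the reader to Table 15, whose rows name 'unlikely' explicitly, and section 6.2.4 sets its own threshold. Both give the same answer. This stands. A reader might infer that expedited reporting depends on which section is consulted, but the documents support that only if someone carries the yes/no label into a table that already names the category.

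A reader might also infer that the planned treatment-related toxicity tables would be distorted. Section 8 plans none. Its analyses are the TITE-CRM on DLTs, locoregional recurrence, overall survival, tumor shrinkage, and longitudinal plots of toxicity and quality-of-life scores, with no attribution filter stated.

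Nor does the related text strictly require plausible timing, which is one of three and/or alternatives. The clash with the definition of 'unlikely' is therefore a strong tension rather than a logical impossibility on that ground alone. The mismatch with Table 15 does not depend on it.

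The reply does not reach the sections in step 4. They name no graded category, so reading Table 15 directly does not resolve them.

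**Conclusion.** The inconsistency is explicit and in current text. One of five attribution categories is grouped as related in 6.1.4 and as not related in Table 15 and 6.2.4. Its practical reach is modest: the type of manufacturer report (same 30-day deadline), follow-up and post-study reporting that turn on relatedness, and any related-event summary the sponsor chooses to produce. A change in expedited reporting is conditional on misapplying the yes/no label and is limited to unexpected SAEs. The DLT, the MTD and the TITE-CRM are unaffected.

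This rests on two assumptions: that the row labels of Table 15 were extracted correctly, although some of its cells may be merged; and that the bare word 'related' elsewhere takes its meaning from the yes/no rule in 6.1.4. The number of events that would be rated 'unlikely' is not given, so the effect on counts cannot be sized.

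**What to change.** In section 6.1.4, move 'unlikely' from the related group to the not-related group. State once that 'related' means possible, probable or definite, and apply that wherever the protocol says 'related' or 'unrelated' and in any summary of related events. Sections 6.1.4, 6.2.3 and 6.2.4 then use one grouping.

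Merely stating that Table 15 governs reporting would settle the routing but leave 6.1.4 at odds with its own definition and the binary-only sections unresolved.

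The cost is a one-line amendment with IRB approval under section 10.5.3, and relabelling of any event already rated 'unlikely' and recorded as related. The five-level ratings themselves need not change. The downside is that fewer events carry the related label than under the present wording; reporting the five-level rating alongside the grouped counts would keep those events visible.

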6.1.5 Expectedness of an Adverse Event

Study investigator or treating physician will be responsible for determining whether an AE is expected or unexpected as indicated in the protocol, informed consent form and/or drug information brochure. Expected adverse events of atezolizumab are those adverse events that are listed or characterized in the package insert (PI) or current investigator brochure (IB).

Unexpected adverse events of atezolizumab are those not listed in the PI or current IB or not identified that are not attributable to radiotherapy. This includes adverse events for which the specificity or severity is not consistent with the description in the PI or IB. For example, under this definition, hepatic necrosis would be unexpected if the PI or IB only referred to elevated hepatic enzymes or hepatitis. An AE will be considered unexpected if the nature, severity, or frequency of the event is NOT consistent with the risk information previously described for the study intervention (atezolizumab and/or radiotherapy).

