6.2.4 Reporting Instructions

- Reporting to Regulatory Authorities, Ethics Committees and Investigators**

Sponsor investigator, as the sponsor of the study, will be responsible for the expedited reporting of safety reports originating from the study to the regulatory authorities (FDA) where it has filed a clinical trial approval, in compliance with local regulations.

Sponsor investigator, as the sponsor of the study, will be responsible for the expedited reporting of safety reports originating from the study to the EMA through Eudravigilance Clinical Trial Module (EVCTM), where applicable.

Sponsor investigator will be responsible for the expedited reporting of safety reports originating from the study to the Ethics Committees and Institutional Review Boards (IRB), where applicable.

Sponsor investigator will be responsible for the distribution of safety information to its own investigators, where relevant, in accordance with local regulations.

- Food and Drug Administration**

An IND safety report will be submitted for any adverse event that meets all three definitions: possibly related to the study drug, unexpected, and serious. If the adverse event does not meet one of the above definitions, it should not be submitted as an expedited IND safety report.

7 Calendar Day Telephone or Fax Report

The Investigator is required to notify the FDA of any fatal or life-threatening adverse event that is unexpected and assessed by the Investigator to be possibly related to the use of atezolizumab. An unexpected adverse event is one that is not already described in the atezolizumab Investigator Brochure. Such reports are to be telephoned or faxed to the FDA and Genentech within 7 calendar days of first learning of the event.

15 Calendar Day Written Report

The Investigator is also required to notify the FDA and all participating investigators, in a written IND Safety Report, of any serious, unexpected AE that is considered reasonably or possibly related to the use of atezolizumab. An unexpected adverse event is one that is not already described in the atezolizumab investigator brochure.

Written IND Safety reports should include an Analysis of Similar Events in accordance with regulation 21 CFR § 312.32. All safety reports previously filed by the investigator with the IND concerning similar events should be analyzed and the significance of the new report in light of the previous, similar reports commented on.

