8.2 Objectives and Analysis Plans

8.2.1 Primary Objective and Analysis Plan

The primary objective of the study is to determine the maximum tolerated dose (MTD) of the DEHART regimen delivered with adjuvant atezolizumab in patients with locally advanced or de novo metastatic HNSCCs.

The MTD will be determined as the radiation dose at which there is a 30% rate of dose-limiting toxicity (DLT) up to 12 months after completion of radiation treatment (to allow for the development of late toxicities from radiation treatment) using the TITE-CRM design.

A DLT will be defined for the purposes of this protocol as an inability to complete radiation treatment within 30 days of the start of radiotherapy not deemed to be related to disease progression or unrelated death, unacceptable toxicity within one year of treatment (Grade 4+ toxicity) probably or definitely related to radiation treatment as deemed by the treating physician, or a death within one year of treatment deemed probably or definitely related to treatment. Expected Grade 3 acute toxicities typical of head and neck radiation, acute dermatitis, acute mucositis, feeding tube placement, electrolyte abnormalities, pain requiring narcotic medication and dehydration requiring IV hydration, resolving within 90 days of treatment will **NOT** be considered DLTs. Grade 4+ late toxicities that may be considered a DLT of reirradiation include but are not limited to:

- Chondronecrosis of the laryngeal cartilages
- Laryngeal edema requiring tracheostomy
- Carotid blowout syndrome or other life-threatening vascular bleed
- Aspiration pneumonia requiring ICU admission not related to tumor progression
- Chronic non-healing wound or soft tissue necrosis requiring flap reconstruction
- Brainstem necrosis
- Radiation myelopathy

Grade 1-3 immune-related toxicity from atezolizumab will not be considered a DLT. Additionally, death deemed unrelated to radiation or atezolizumab (such as death due to malignancy or other comorbidity) will not be considered a DLT.

All patients who initiate radiation therapy will be evaluable for the primary endpoint as long as they initiate radiation therapy.

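### Sections 6.1.5 and 6.2.4 use different tests of expectedness and Table 15 does not say which applies, so some serious events related to both treatments have contradictory FDA reporting duties

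*Combined protocol and SAP*

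**What the plan says.** **Section 6.1.5** contains four statements on expectedness.

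- The investigator or treating physician decides "whether an AE is expected or unexpected as indicated in the protocol, informed consent form and/or drug information brochure".
- For the drug, "Expected adverse events of atezolizumab are those adverse events that are listed or characterized in the package insert (PI) or current investigator brochure (IB)".
- The converse is not a mirror image: "Unexpected adverse events of atezolizumab are those not listed in the PI or current IB or not identified that are not attributable to radiotherapy".
- A closing sentence makes any event unexpected if its nature, severity or frequency does not fit the risk information already described for atezolizumab and/or radiotherapy.

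**Section 6.2.4** governs FDA reports and sets its own test, given for both the 7-day and the 15-day report: "An unexpected adverse event is one that is not already described in the atezolizumab Investigator Brochure". A report is due when an event is possibly related to the study drug, unexpected and serious. It adds: "If the adverse event does not meet one of the above definitions, it should not be submitted as an expedited IND safety report".

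**Table 15 (section 6.2.3)** shows FDA reporting, and IRB reporting within 5 calendar days, only for unexpected SAEs that are possibly, probably or definitely related. Footnote 3 explains the slower route: "For routine reporting, the events will be reported to IRB as part of the annual continuing progress report". Footnote 4 sends the reader to 6.2.3 for detailed instructions, although the FDA instructions and their definition of unexpected are in 6.2.4.

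**Section 6.1.4** requires causality to be judged separately for each protocol therapy, so one event can be related to both.

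**The concern.** The trial delivers a new radiotherapy regimen followed by atezolizumab, so toxicity to which both contribute is a risk that oversight bodies would want to hear about promptly. Whether they do depends on the word unexpected, and the protocol defines it in two ways.

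The radiotherapy exception in 6.1.5 matters most for a serious event attributed to both treatments. It takes the event out of the drug's unexpected category because radiotherapy also contributed, even though the brochure may say nothing about it. Section 6.2.4 has no such exception. Two staff members who each follow the protocol correctly could reach opposite conclusions about whether FDA must be told.

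Reporting everything to be safe is not clearly open either. If 6.1.5 is taken as the definition, the event fails one of the three conditions and 6.2.4 says not to send an expedited report.

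**Working it through.** The plan gives no figure to reproduce. The check is a side-by-side reading, followed by a bound on the number of DLTs that could be affected.

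**Traced event.** Take a fatal carotid bleed at month 5, judged probably related to radiotherapy and possibly related to atezolizumab. Section 8.2.1 lists "Carotid blowout syndrome or other life-threatening vascular bleed" among Grade 4+ late toxicities that may count as DLTs. Assume the event fits the described radiotherapy risk and is not in the atezolizumab brochure. The brochure is not among the documents; none of the seven late toxicities listed in 8.2.1 appears in the atezolizumab risk list in 7.4.2.

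| Step | Using 6.1.5 | Using 6.2.4 |
|---|---|---|
| Reference | Protocol, consent form, package insert or brochure; radiotherapy-attributable events excepted | Atezolizumab brochure only |
| Classification | Expected, or at least not an unexpected atezolizumab event | Unexpected |
| FDA | None in Table 15 | 7 calendar days (15 for a serious event that is neither fatal nor life-threatening) |
| IRB through Table 15 | No 5-day report; apparently routine annual review | 5 calendar days, if Table 15 uses this definition |

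The routine IRB entry is an inference: in the available text the expected-SAE cells of the related row are blank, probably merged with the row above. The absence of FDA from those cells does not depend on that inference.

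**Which events conflict.** Four conditions must hold together: the event is serious, consistent with described radiotherapy risk, absent from the brochure, and at least possibly related to atezolizumab. If the event is in the brochure and fits it, both sections call it expected. If it is absent from the brochure and does not fit the described radiotherapy risk, the closing sentence of 6.1.5 can make it unexpected, and the sections agree.

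**Bound on DLTs.** Inputs: 18 patients and a 30% DLT rate up to 12 months after radiotherapy (8.1); constant DLT hazard and median survival of 17 months with constant hazard (8.3); atezolizumab no earlier than 28 days after fraction 1 (5.2). Assume 21 days of radiotherapy, a window of 21 + 365 = 386 days, and months of 30.44 days.

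- Expected DLTs, ignoring deaths: 18 × 0.30 = 5.4.
- Daily DLT hazard: −ln(0.70)/386 = 0.000924.
- Share before day 28: (1 − exp(−0.000924 × 28))/0.30 = 8.5%. After day 28: 5.4 × 0.915 = 4.9.
- Daily death hazard: ln 2/(17 × 30.44) = 0.00134. Total hazard: 0.000924 + 0.00134 = 0.00226. DLT share of the total: 0.408.
- Probability that a DLT is observed before death: 0.408 × (1 − exp(−0.00226 × 386)) = 0.408 × 0.583 = 0.238. In 18 patients: 4.3.
- Of these, before day 28: 18 × 0.408 × (1 − exp(−0.00226 × 28)) = 0.45. After day 28: 4.28 − 0.45 = 3.8.

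So about 4 to 5 DLTs (3.8 to 4.9) would fall after atezolizumab may begin. Only those that also meet the four conditions are affected.

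**The case against.** **The closing sentence of 6.1.5 is a backstop.** A reader might infer that any event attributable to radiotherapy is automatically expected, so that combined toxicity could never be unexpected. The text does not support that. The exception limits only unexpected events of atezolizumab, and an event of unusual nature, severity or frequency can still be unexpected under the general test. The and/or in that test can also be read as making inconsistency with either treatment sufficient. This stands, and it is why the conflict covers a subset.

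**Section 8.2.1 does not label late DLTs as expected.** It uses that word only for Grade 3 acute toxicities. A reader might infer that naming late toxicities there makes them expected in advance, because 6.1.5 allows the protocol as a source. That is a possible use of 6.1.5, not something 8.2.1 says.

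**Section 6.2.4 carries its own definition.** Applied alone, it sends the traced event to FDA, and its bar on submission bites only if the 6.1.5 test is imported. That is a fair reading of 6.2.4. But Table 15 also sets the FDA duty and names neither test, so the protocol does not establish which reading governs.

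**The IRB has other routes.** Section 8.4 sends unanticipated or severe radiation toxicity to the IRB under institutional guidelines and DLTs to the DSMC within 5 calendar days; 6.3 applies institutional policy on unanticipated problems. It would therefore be wrong to say that the IRB hears only once a year. These routes soften the IRB gap. They do not settle the FDA duty.

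**Separate causality does not require separate expectedness.** These are different judgements. Section 6.1.4 matters here only because it permits attribution to both treatments.

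**Conclusion.** The concern holds in limited form. The protocol has two expectedness tests with different reference documents, and for the subset described they give opposite answers on whether FDA must receive an expedited report. The IRB discrepancy is less certain because it rests partly on blank table cells and is softened by 8.4 and 6.3.

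The number of events affected is unknown. The 4 to 5 DLTs are a ceiling for DLTs under the 30% target rate, 18 patients and constant hazards, not a forecast. The share also judged possibly related to atezolizumab is not given, and failure to complete radiotherapy within 30 days, which also counts as a DLT, would not follow a constant one-year hazard. Serious events that are not DLTs could also be affected and are not counted. The conclusion also assumes that the brochure does not describe the event.

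This should be corrected, because a contradiction that can delay or suppress an expedited safety report is more than a missing detail. It does not affect the MTD estimate or the sample size.

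**What to change.** 1. In 6.1.5, delete the radiotherapy exception from the sentence defining unexpected atezolizumab events.
2. State there that, for any event at least possibly related to atezolizumab, expectedness for FDA reporting is judged against the current atezolizumab brochure, whether or not the event is also attributed to radiotherapy.
3. State that listing as a possible DLT in 8.2.1 does not by itself make an event expected.
4. Name the reference document for radiotherapy risk. It should not be only the Grade 3 acute list in 8.2.1, since every late radiation SAE would then become unexpected.
5. Tie Table 15 to this definition, point footnote 4 to 6.2.4, and make explicit what the related, expected SAE cells require for the IRB.
6. Keep expedited FDA reporting conditional on at least possible relation to atezolizumab, so that Table 15 does not contradict 6.2.4 for events due to radiotherapy alone.

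The cost is a few sentences in 6.1.5, Table 15 and 6.2.4, and probably a few extra expedited reports over the trial.
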